4.4 Visit Schedule and Definition of Week for Analysis Purposes

The Step 1 visit schedule for key study outcomes is shown in Table 1 below. The protocol requires evaluations to be scheduled at week 1 (± 3 days), week 4 (± 7 days), week 12, 24 and 36 (± 14 days), week 48 (-14 days, +3 days), *week 49 (-3 days, +14 days), and weeks 60 and 72 (± 42 days).

***NOTE:** The week 49 visit is optional, in the event that blood volumes were not sufficient at the week 48 visit.

Telephone evaluations will occur at week 2 (± 3 days), week 8 (± 7 days) and at weeks 60 and 72 the day following performance of the gut biopsy and/or lumbar puncture optional procedures.

For the purposes of analysis, visit windows will be formed around each study visit using the midpoints between adjacent weeks as cutoffs, and potentially including assessments collected outside the recommended visit windows described above. If there are multiple evaluations within the analysis window for a given visit, the evaluation closest to the scheduled study week will be used, and the earlier measurement will be used if there are two measurements that are equally distant from the scheduled week.

Table 1 on the next page details the analysis windows for the data collected on Step 1.

Table 1: Study Visit Schedule and Analysis Windows for Step 1

Evaluation	Entry	Post-Entry Evaluations (Weeks)								
	0	1	4	12	24	36	48	49*	60	72
Analysis window		1-14 days	15-56 days	57-126 days	127-210 days	211-294 days	295-378 days		379-462 days	463-546 days
Fiebig Staging	X									
Clinical Assessment	X	X	X	X	X	X	X		X	X
Complete Physical Exam	X									
Targeted Physical Exam		X	X	X	X	X	X	X	X	X
Height	X									
Weight	X	X	X	X	X		X	X	X	X
Hematology, Chemistries, LFTs	X		X	X	X		X		X	X
CD4+/CD8+ T-cells	X			X	X		X		X	X
PBMC and Plasma Storage	X		X	X	X		X	X	X	X
Plasma HIV-1 RNA	X		X	X	X	X	X		X	X
Total HIV-1 DNA by qPCR	X						X	X		
Adherence Assessment		X	X	X	X	X	X	X	X	X
Leukapheresis (optional)	X									X
Large Volume Blood Collection (optional)	X									X
Gut Biopsy (optional)										X
Lumbar Puncture (optional)										X

*NOTE: The week 49 visit is optional, in the event that blood volumes were not sufficient at the week 48 visit.

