6.3.3 Post-Entry Evaluations

All post-entry evaluations occur in reference to the date of ART initiation.

On-ART Step 1 Evaluations

The on-treatment visits have the following window:

- Weeks 1 and 2 (± 3 days) **for all participants**
- Weeks 4 and 8 (± 7 days) **for all participants**
- Weeks 12 and 24 (± 14 days) **for all participants**
- **Week 36 (± 14 days)**
- Week 48 (-14 days through +3 days)
- Week 49 (**optional, if needed to achieve blood volume collection goal at week 48**; -3 days through +14 days)
- week 60 and 72 (± 42 days)

Step 1 Telephone Evaluations

Evaluations that are scheduled for weeks 2 and 8 **on Step 1** will be completed by the site staff via telephone (in lieu of an in-person visit by the participant) and documented on the electronic case report form (eCRF). Site staff will call the participant to inquire about recent Grade ≥ 2 AEs and provide adherence counseling. If any Grade ≥ 2 AEs that require further investigation are reported, the participant may be asked to present for in-person evaluation. Follow-up phone calls may be indicated. Site staff may use the telephone script provided

in the A5354 MOPS as guidance and for documentation of the telephone encounter(s).

NOTE: The day following the optional gut biopsy via flexible sigmoidoscopy and/or lumbar puncture procedures to be performed between weeks 60 and 72, site staff will contact the participants via telephone to inquire how they are feeling, which will be documented on the eCRF ([refer to section 6.4.11](#) for additional information). If any symptoms are present on the day of the initial telephone call, follow-up phone calls to the participants are recommended. Site staff must ensure that the follow-up phone calls are completed as part of the **follow-up of optional procedure** evaluations.

Step 2 Evaluations

The Step 2 Registration evaluation may be combined with the Step 1 Week 72 visit. If the Step 2 Registration visit is not combined, then all Step 2 evaluations must be performed within 2 weeks after the final Step 1 visit. Those participants re-enrolling into the study after going off study at week 72 under protocol Version 1.0 will complete all evaluations listed in the Step 2 Registration column.

All visits following Step 2 registration will have a \pm 60-day visit window.

Study Completion Evaluations

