The **week 24 visit on Step 1** will be the final study visit for participants who initiated ART during Fiebig VI (**based on confirmed Fiebig stage results**), and **these participants will be replaced. For Step 2, the final visit will occur at week 144 for all the study groups, except in cases of premature study discontinuation as described in [section 6.3.5](#).** Upon study completion, ART will no longer be provided through the study (i.e., post-trial access to ART is not within the scope of A5354). The study team will ensure that participants are referred to appropriate health facilities to continue their ART. After the study ends, ART regimens may be modified according to local practices and decision by the participants and their physicians.

6.3.4 Confirmation of Virologic Failure (VF) Evaluation on Step 1 and Step 2

VF is defined as having two consecutive HIV-1 RNA >200 copies/mL **24 weeks or more after study entry**, or at any time after achieving HIV-1 RNA <50 copies/mL. A confirmatory plasma HIV-1 RNA measurement **and other evaluations per [sections 6.1](#) and [6.2](#)** should be done as soon as possible, ideally within 7 to 14 days of the initial sample with a HIV-1 RNA >200 copies/mL. If the visit for HIV-1 RNA confirmation coincides with a regularly scheduled visit, the evaluations should be combined. **Refer to [section 6.3.5](#) for instructions on the discontinuation evaluations for participants who have confirmed VF. Participants who interrupt ART for ≥ 7 consecutive days prior to meeting criteria for VF should be managed per [section 6.3.6](#).**

NOTE: If genotyping is performed as part of routine care, then the results will be documented in the eCRF. Stored blood may be used for additional genotype testing for research purposes.

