10.0 STATISTICAL CONSIDERATIONS

10.1 General Design Issues

This is a prospective, open-label study to measure the effects of early ART on the establishment of HIV-1 reservoir and HIV-1-specific immunity. Participants with AHI will have an enrollment visit and initiate ART at the time of enrollment. Each participant will be followed **on study** for up to **216 weeks (72 weeks on Step 1 and 144 weeks on Step 2)** unless they are Fiebig VI at ART initiation in which case their last visit will be **no later than week 24 on Step 1**. The primary endpoint is CAHD in 5 million blood-derived CD4+ T-cells assayed by qPCR at week 48 **on Step 1**. Only participants who have not met criteria for permanent study discontinuation, have not missed more than 6

consecutive days of ART and have HIV-1 RNA <50 copies/mL at week 48 **on Step 1 will be included in the primary efficacy analysis**. If adequate sample and analyzable data are not available from the week 48 visit, week 49 will be used instead.

Characterization of Fiebig stage using samples at the time of ART initiation will be performed with results known within 12 weeks based on standardized, centralized testing; this will define the analysis groups. **Each study group had a target enrollment of 50 participants under protocol Version 1.0. Study Groups 2 and 3 have reached their target enrollment and therefore the original inclusion criteria from protocol Version 1.0 corresponding to these groups are no longer applicable for eligibility into the study.** Because Fiebig stage for the analysis comparison will not be known until after therapy is initiated, over-enrollment based on available data at the time of entry may be implemented.

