17.1 Primary Efficacy Analyses

Note: Programs related to the analysis of the primary outcome measures listed in this section will require validation in accordance with the CBAR SOP, PROG.10083, including independent verification of results

A table summarizing completeness of the primary outcome measure, and reasons for missing data (if any) will be provided, overall and by study group.

Analysis of the primary outcome measure will be restricted to participants who maintain HIV-1 RNA <50 copies/mL at week 48 with no ART interruption of ≥ 7 consecutive days and have available CAHD results from week 48 or week 49. Specifically, plasma HIV-1 RNA by commercial assay must be <50 copies/mL at week 48 with no prior virologic failure (defined as having two consecutive HIV-1 RNA >200 copies/mL at week 24 or later or at any time after achieving HIV-1 RNA <50 copies/mL). This study is designed to evaluate the effect of suppressive ART initiated in different stages of AHI on the establishment and persistence of HIV-1 reservoirs; this is the rationale for analyzing HIV-1 DNA only among virally suppressed participants and not in those with incompletely suppressed viremia (≥ 50 copies/ml).

Participants who are excluded from the primary analysis will be presented in a listing, which displays the criteria by which they were excluded.

The primary outcome measure will be summarized as a binary outcome, [0 copies] versus [>0 copies] of CAHD per 5 million CD4+ T-cells, assessed separately and jointly by gag- and integrase-assays. In order for a participant to be considered as having 0 copies of CAHD, the participant must be found to have an undetectable CAHD result from both assays. The proportion of participants with '0 copies of CAHD' will be compared pairwise between groups using Fisher's exact test. A 95% confidence interval for the proportion estimated will be calculated using the exact binomial distribution. The analysis groups will be the study groups: Group 1 (Fiebig I/II), Group 2 (Fiebig III/IV), and Group 3 (Fiebig V), as defined by the results of the centralized testing from samples at study entry.

CAHD per million CD4+ T-cells will also be summarized as a continuous variable, separately for gag- and integrase-assays, presenting N, median, Q1 and Q3 for the raw CAHD values (by study group and separately by Fiebig Stage). CAHD per 5 million CD4+ T-cells will be divided

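### The SAP's closest-to-schedule rule is not switched off for the week-48 HIV-1 RNA that defines the primary population, so a repeat test can qualify CAHD drawn during viraemia

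*SAP*

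**What the plan says.** SAP 4.4 builds analysis windows from the midpoints between adjacent scheduled weeks, "potentially including assessments collected outside the recommended visit windows described above". Table 1 there gives week 48 the window of days 295-378. When several results fall in a window, "If there are multiple evaluations within the analysis window for a given visit, the evaluation closest to the scheduled study week will be used"; for ties, "the earlier measurement will be used if there are two measurements that are equally distant from the scheduled week". The rule is general, and no variable is exempted.

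SAP 17.1 defines the primary population: "Specifically, plasma HIV-1 RNA by commercial assay must be <50 copies/mL at week 48 with no prior virologic failure". It also requires no ART interruption of 7 or more consecutive days and a CAHD result from week 48 or week 49. SAP 4.3 and Protocol 10.6 say essentially the same. SAP 17.1 gives the reason: DNA is to be studied under suppressive ART, so participants with RNA of 50 copies/mL or more are left out. None of these sections says that the qualifying RNA must come from the visit at which the CAHD blood was drawn.

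Protocol 6.3.3 allows the week-48 visit from 14 days before to 3 days after the target day. Protocol 6.3.4 defines virologic failure as two consecutive RNA values above 200 copies/mL, either from week 24 onward or after RNA below 50 has been reached. It asks for a confirmatory RNA as soon as possible, "ideally within 7 to 14 days of the initial sample with a HIV-1 RNA >200 copies/mL".

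**The concern.** The protocol itself generates the second RNA that lets the 4.4 rule go wrong. The week-48 visit window leans early, so a repeat prompted by a high value at that visit will often land nearer day 336 than the visit did. If the repeat is below 50, the SAP takes it as the week-48 RNA. A single value above 200 followed by a low one is not virologic failure, so that exclusion does not catch the participant. The CAHD specimen stays with the visit: the failure-confirmation column of the Step 1 schedule lists plasma RNA but neither PBMC storage nor total HIV-1 DNA.

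The result is a specimen taken during viraemia and analysed as suppressed. The plan's other checks would not reveal it. The SAP 17.1 listing covers only excluded participants. Double coding (SAP 4.5) would apply the same rule twice. The sensitivity analysis that readmits ART interruptions keeps the same week-48 RNA criterion.

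**Working it through.** **Inputs.** Week 48 is day 336 (48 × 7). Visit days are 336 − 14 = 322 to 336 + 3 = 339, which is 18 days (Protocol 6.3.3). Repeat delay r is 7 to 14 days, which is 8 values (Protocol 6.3.4). The planned evaluable number is 42 per group, tested by Fisher's exact test at 0.05 per pairwise comparison (Protocol 10.4).

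**The plan's own figures reproduce.**
- Window: the midpoint of days 252 and 336 is 294, and of days 336 and 420 is 378. This gives days 295-378, as in SAP Table 1.
- Power: exact two-sided Fisher power at 42 per group for 65% versus 35% is 76.3%, against the stated 76%.

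**A worked case.** CAHD and RNA are drawn on day 325, with RNA 400. The repeat on day 336 is below 50. There has been no ART interruption of 7 days or more. The distances from day 336 are 11 and 0, so the repeat is the week-48 RNA. There are not two consecutive values above 200, so there is no failure. The day-325 CAHD is analysed.

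**When displacement occurs.** Let the draw be k days before day 336. The repeat is nearer when |r − k| < k, that is, when r < 2k. A tie keeps the earlier value.

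| Draw day | k | Delays (of 8) that displace |
|---|---|---|
| 322-328 | 14 to 8 | 8 each, 56 in all |
| 329 | 7 | 7 |
| 330 | 6 | 5 |
| 331 | 5 | 3 |
| 332 | 4 | 1 |
| 333-339 | 3 to −3 | 0 |

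Total: 56 + 7 + 5 + 3 + 1 = 72 of 18 × 8 = 144 combinations, on 11 of the 18 visit days.

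**Sensitivity of the count.** Protocol visits are timed from ART start, while SAP 4.1 and 4.2 count from study entry. If ART starts 1 or 2 days after entry, the count becomes 64 or 56. The 7-14 day interval is an ideal. By delay, displacement affects 11 of 18 visit days at 7 days, 7 at 14 days, 4 at 21 days and none at 28 days.

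**Effect of one participant.** Adding one person with detectable CAHD to a group of 42, at the Protocol 10.4 planning rates for undetectable CAHD:
- 75%: 31.5/43 = 73.3%, a change of −1.7 points
- 25%: 10.5/43 = 24.4%, a change of −0.6 points
- 3.5%: 1.47/43 = 3.4%, a change of −0.1 points

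**Power if such participants are removed from 42 per group** (assumed range; the documents give no number):

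| Removed per group | 75% v 25% | 65% v 35% |
|---|---|---|
| 0 | 99.7% | 76.3% |
| 1 | 99.6% | 74.4% |
| 2 | 99.5% | 72.4% |
| 4 | 99.2% | 68.0% |

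**A borderline illustration.** For Fiebig III/IV versus V, hypothetical counts of 9/41 versus 2/42 undetectable give Fisher p = 0.026. Adding one viraemic participant with detectable DNA (9/42 versus 2/42) gives p = 0.048.

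**The case against.** The strongest reply is that pairing is already the default. RNA and total HIV-1 DNA are both scheduled at week 48, and no other scheduled RNA lies nearer day 336. The only protocol-driven competitor is the failure-confirmation test, which needs a value above 200. At 50-200 copies/mL no repeat is prompted, so the visit-day value stands and the participant is excluded as intended. All of this is correct. It limits how often the problem arises but does not close the gap.

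One may also say that maintaining RNA below 50 implies more than one value. But the next sentence of SAP 17.1 spells the requirement out as the week-48 value plus no prior failure.

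Three stronger readings are tempting, and the documents do not support them.

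- **That half of those with a high visit-day value are misclassified.** The 72 of 144 weights visit days and delays equally. It also ignores a necessary condition: the repeat must be below 50. A repeat of 50-200 still excludes the participant, and a repeat above 200 confirms failure.
- **That suppressed participants are wrongly excluded in the same way.** This needs an unscheduled viraemic RNA nearer day 336. The protocol calls for no further RNA there after a suppressed draw.
- **That week-49 CAHD lacking a same-day RNA is the same error.** Protocol 10.1 provides for it: "If adequate sample and analyzable data are not available from the week 48 visit, week 49 will be used instead". The inclusion rules explicitly combine a week-48 RNA with CAHD from week 48 or week 49. The gap can reach 357 − 322 = 35 days at the extreme, but that is a design choice, and changing it would need new testing.

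**Conclusion.** The point holds in a narrow form. Followed literally, SAP 4.4 can admit to the primary analysis a CAHD specimen drawn at RNA above 200 copies/mL, which SAP 17.1 says should not be analysed. It requires a week-48 visit on days 322-332, a repeat nearer day 336, and a repeat result below 50.

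The number affected is probably 0-2. This is a judgement, since the documents give no rate of isolated high values. If 1-3% of about 126-150 participants had one at the visit, that would be roughly 1-5 people, and only some of them would meet the other conditions. At the planning rates, one such person moves a group by at most about 1.7 points, and the 75% versus 25% comparison is essentially unaffected. A closer result could be more sensitive.

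The case for acting is that the rule contradicts the plan's stated purpose, and that settling it now avoids a case-by-case decision once CAHD results are known.

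**What to change.** In SAP 4.3 and 17.1, state that the suppression criterion is exempt from the 4.4 selection rule. The qualifying RNA is the one drawn at the same visit as the week-48 CAHD specimen, whatever other RNA results fall in the window. Use the 4.4 rule only if that RNA is missing.

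For CAHD from week 49, or from blood pooled across weeks 48 and 49 (allowed by Protocol 6.4.8), use the week-48 visit RNA, as the plan already intends. List the RNA and CAHD dates for every included participant, so that any mismatch is visible.

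With the visit-day RNA available, displacement falls from 72 of 144 combinations to none. The cost is a few SAP sentences, one changed derivation and one listing, with no new testing. The downside is that one or two participants may leave or join the primary population.

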4.5 Validation of Programs

All programs used to create datasets used for analyses detailed in this SAP will be validated following the CBAR SOP, PROG.10083, for both interim analyses for SMC review and for the primary analysis. Validation of analysis programs following CBAR SOP, PROG.10083, will be undertaken for analyses addressing the study's primary objective and key secondary objectives; these analyses are indicated in the relevant sections below.

Furthermore, per CBAR SOPs (PROG. 10083), analyses and datasets contributing to the primary objective will be independently programmed ("double coded"). This includes all analyses, outcome measures and covariates detailed in Section 17 of this document.

5 ACCRUAL

Table: Number enrolled by study group showing, if applicable, number with eligibility violations and exclusions from analysis.

List (if applicable): Description of violations of eligibility criteria, and details of exclusions from analyses (including participants who are HIV Negative and Fiebig VI).

Tables: Number (%) enrolled by month/year of enrollment: cross-tabulation by study group. Dates of first and last enrollments will be provided in a footnote to the table.

Table: Number (%) enrolled by country/site: cross-tabulation by study group.

6 BASELINE CHARACTERISTICS

Tables: Showing following variables:

Demographic and enrollment information:

- a. Sex: number (%).
- b. Gender identity: number (%)
- c. Participant reported race and ethnicity: number (%) by category used in eligibility screening.
- d. Age on the day of study entry (years): N, median and 25th and 75th percentiles, min, max; number (%) by age group (18-29, 30-39, 40-49, 50+; years, rounded down).
- e. IV drug use: number (%) by category (never used, previously used, current user).
- f. Self-reported risk of HIV exposure: number (%) by category (Homosexual contact, heterosexual contact, injectable drug use, unknown/not reported)

Health status information:

- a. HIV-1 RNA (copies/ml): N, number (%) by category (<40, 40-<1,000; 1,000-<10,000; 10,000-<100,000; 100,000-<1,000,000; 1,000,000-<10,000,000; ≥10,000,000)
- b. HIV-1 RNA (log₁₀ copies/ml): N, mean, standard deviation, median and 25th and 75th percentiles, min, max
- c. CD4+, CD8+ cell count (cells/mm³): N, mean, standard deviation, median and 25th and 75th percentiles, min, max; number (%) by category (<50, 50-199, 200-349, 350-499, ≥500.)

- d. CD4/CD8 ratio: N, mean, standard deviation, median and 25th and 75th percentiles, min, max
- e. BMI (kg/m²): N, mean, standard deviation, median and 25th and 75th percentiles, min, max; number (%) by category (underweight [<18.5]; normal [$18.5- <25$], overweight [$25- <30$]; obese [≥ 30])
- f. HIV symptoms at AHI identification (symptomatic; asymptomatic): N, number (%)
- g. Hospitalization status at AHI identification (hospitalized; not hospitalized): N, number (%)
- h. Alanine Aminotransferase and Aspartate Aminotransferase (U/L): N, mean, standard deviation, median and 25th and 75th percentiles, min, max;
- i. Hematocrit (%): N, mean, standard deviation, median and 25th and 75th percentiles, min, max
- j. Hemoglobin (g/dL): N, mean, standard deviation, median and 25th and 75th percentiles, min, max
- k. Platelets (cells/mm³): N, mean, standard deviation, median and 25th and 75th percentiles, min, max
- l. Leukocytes (cells/mm³): N, mean, standard deviation, median and 25th and 75th percentiles, min, max
- m. Creatinine clearance (mL/min): N, mean, standard deviation, median and 25th and 75th percentiles, min, max

For Females:

- n. Pregnancy test result (positive, negative, not of reproductive potential): N, number (%)
- o. Breast-feeding status (no, yes): N, number (%)

For individuals with genotype results reported from SOC:

- p. HIV subtype (B, C, CRF#, etc.): N, number (%)
- q. HIV genotype drug resistance interpretations (Susceptible, Intermediate, Resistant, Not Reported) for each of the drugs reported: N, number (%)

NOTE: Due to the variety of genotype results reported, interpretations for a given drug may not be available for all participants

7 FIEBIG STAGE

Tables showing the following:

- a. Cross tabulation of the study group estimated at entry, and that determined by centralized testing: number (%)
- b. Time (weeks) between study entry and Fiebig stage results (latest assay date) determined by centralized testing: N, mean, standard deviation, median and 25th and 75th percentiles
- c. Time (weeks) between screening and study entry: N, mean, standard deviation, median and 25th and 75th percentiles

- d. Fiebig stage determined by centralized testing: number (%) overall and by country
- e. Listing: Participants found to be HIV negative after enrollment, showing estimated Fiebig group at screening, screening assay timing/results, centralized assay timing/results, components and duration of ART regimen taken (if applicable), HIV-1 RNA assay results, site, and duration on study

